5.2 Contraception Recommendations

Contraception Requirements for Females

Subjects must follow the following contraceptive guidelines as specified:

- Females, Nonchildbearing Potential

Females do not need to use birth control during or following study drug treatment if considered of nonchildbearing potential due to meeting any of the following criteria:

1. Premenopausal female with permanent sterility or permanent infertility due to 1 of the following:
 - Permanent sterility due to a hysterectomy, bilateral salpingectomy, or bilateral oophorectomy.
 - Nonsurgical permanent infertility due to Mullerian agenesis, androgen insensitivity, or gonadal dysgenesis; investigator discretion should be applied to determining study entry for these individuals.
2. Postmenopausal female
 - Age $>$ 55 years with no menses for 12 or more months without an alternative medical cause.
 - Age \leq 55 years with no menses for 12 or more months without an alternative medical cause AND a follicle-stimulating hormone (FSH) level \geq 30 IU/L.
- Females, of Childbearing Potential
 - Females of childbearing potential must avoid pregnancy from Study Day 1 through 12 weeks after the last dose of study drug.
 - Females must commit to 1 of the following methods of birth control:
 - Combined (estrogen and progestogen containing) hormonal birth control (oral, intravaginal, transdermal, injectable) associated with inhibition of ovulation-initiated at least 30 days prior to study Day 1 (baseline).
 - Progestogen-only hormonal birth control (oral, injectable, implantable) associated with inhibition of ovulation initiated at least 30 days prior to study Day 1 (baseline).
 - Bilateral tubal occlusion/ligation (can be via hysteroscopy, provided a hysterosalpingogram confirms success of the procedure).
 - Intrauterine device.
 - Intrauterine hormone-releasing system.
 - Vasectomized partner (provided the partner has received medical confirmation of the surgical success of the vasectomy and is the sole sexual partner of the trial subject).
 - Practice true abstinence, defined as: Refraining from heterosexual intercourse when this is in line with the preferred and usual lifestyle of the subject (periodic abstinence [e.g., calendar, ovulation, symptothermal, post-ovulation methods] and withdrawal are not acceptable).

Contraception recommendations related to the use of concomitant therapies prescribed should be based on the local label.

- Progestogen-only oral hormonal contraception, where inhibition of ovulation is not the primary mode of action, initiated at least 30 days prior to study Day 1 (baseline).
- Male or female condom with or without spermicide.
- Cap, diaphragm, or sponge with spermicide.

- A combination of male condom with cap, diaphragm, or sponge with spermicide (double-barrier method).

Contraception Requirements for Males

Male subjects who are sexually active with a female partner of childbearing potential must agree to use male condoms, even if the male subject has undergone a successful vasectomy, from study Day 1 (baseline) through 12 weeks after the last dose of study drug.

5.3 Prohibited Medications and Therapy

During the study (from informed consent to the completion of double-blind treatment period, blinded extension period, or PD visit, unless otherwise specified), the following medications and therapies are prohibited:

- Psychotropic drugs from the start of washout period to the last dose of study drug except rescue medications listed in Section 5.4
- Drugs, supplements, and foods that inhibit or induce CYP3A4 activity
- Electroconvulsive therapy
- Epinephrine
- Lemborexant from the start of washout period to the last dose of study drug
- Other investigational products

The name, daily dose, administration route, treatment period, and reason for use of antipsychotic drugs prescribed during the 12 weeks before the start of study treatment will be recorded in the case report form (CRF).

For the safety follow-up period, see Section 4.1.

5.4 Prior and Concomitant Therapy

Any medication or vaccine (including COVID-19 vaccine, over-the-counter or prescription medicines, vitamins, and/or herbal supplements) that the subject is receiving at the time of Visit 1 (screening) or receives during the study must be recorded from 28 days prior to study drug administration through the post-treatment visit (Safety Follow-Up [SFU] Week 32).

Any questions regarding concomitant or prior therapy should be raised to the AbbVie emergency contact. Information regarding potential drug interactions with cariprazine can be located in the current cariprazine Investigator's Brochure.

Subjects must be able to safely discontinue any prohibited psychotropic drugs (except for rescue medicine) and epinephrine as follows:

- Oral medicine, patch medicine, intravenous injection, or intramuscular injection within 7 days or 5 half-lives of the drug, whichever is shorter, prior to the first dose of study drug
- Depot LAI antipsychotics, at least longer than label-specified dose interval (e.g., aripiprazole LAI: 4 weeks, etc.) prior to the first dose of study drug

Subjects must be consented for the study prior to discontinuing any prohibited medications for the purpose of meeting study eligibility.

Rescue Medications

Medically appropriate episodic use (up to 3 days) of narcotic analgesics for acute medical indications (e.g., tooth extraction) is allowed during the study. Rescue medication may be changed. The following rescue medications will be allowed from after informed consent to the last dose of study drug according to stipulation for each medication.

For the safety follow-up period, see Section [4.1](#).

For insomnia, monotherapy of the following will be allowed, but should not be prescribed prophylactically. Two or more concurrent use is not allowed:

- Zolpidem (maximum of 10 mg/day)
- Zolpidem extended release (maximum of 12.5 mg/day)
- Zaleplon (maximum of 20 mg/day)
- Eszopiclone (maximum of 3 mg/day)
- Zopiclone (maximum of 7.5 mg/day)
- Suvorexant (maximum of 20 mg/day)

These medications must be administered before bedtime as recommended in their prescribing information. The medication must be documented on the relevant electronic case report form (eCRF). No such medication is permitted within 8 hours of psychiatric or neurological assessments.

For EPS or akathisia, the following will be allowed but should not be prescribed prophylactically:

For EPS or akathisia that emerge or worsen during the study, use of one or more concurrent rescue medications listed below will be allowed. However, each of the 3 EPS scales (AIMS, BARS, and SAS) should be administered first to support the decision to dispense these rescue medications. The only exception to administering the EPS scales before dispensing rescue medication is medical urgency (e.g., dystonia, severe akathisia, etc.).

- Benztropine
- Diphenhydramine
- Propranolol
- Biperiden

- Trihexyphenidyl

The need for continued use of these medications should be regularly assessed by the investigator and documented appropriately.

Injectable agents are not allowed, except for the treatment of an acute dystonic reaction if deemed necessary.

Rescue medications for agitation, restlessness, and hostility:

Episodic use of lorazepam up to 2 mg/day (or equivalent benzodiazepine; one or more concurrent use and either orals or injectables also allowed) and for up to 3 consecutive days at a time is allowed for agitation, restlessness, and hostility. The medication use and the agitation, restlessness, or hostility must be documented on the relevant eCRF pages.

Efficacy assessments should not be performed within 8 hours of administration of lorazepam or equivalent benzodiazepine or within 24 hours of administration of diazepam.

Abrupt discontinuation of benzodiazepines is not advised.

COVID-19 Pandemic-Related Vaccination Guidance

Given the ongoing COVID-19 pandemic, selected non-live vaccines (e.g., mRNA, nonreplicating viral vector, protein subunit, etc.) to prevent SARS-CoV-2 infection may be administered during Visit 1 (screening), the treatment periods, or the safety follow-up period, as long as components of the vaccine are not contraindicated. The first dose of study drug cariprazine, when possible, is preferred to be given at least \pm 7 days from the SARS-CoV-2 vaccine administration. Note: The above guidance applies to all SARS-CoV-2 vaccine doses given as part of the complete vaccination course.

The decision to receive a locally available vaccine should be based on local guidance and an individual discussion between the treating physician and the subject.

These recommendations may be subject to change based on the evolving knowledge around the use of SARS-CoV-2 vaccines in patients with schizophrenia and as more data are collected in real-world scenarios and clinical trials.

Any SARS-CoV-2 vaccine information must be documented on the COVID-19 vaccine eCRF. Refer to the Operations Manual for instructions on reporting any AEs associated with the COVID-19 vaccine.

5.5 Withdrawal of Subjects and Discontinuation of Study

A subject may voluntarily withdraw or be withdrawn from the study drug at any time for reasons including, but not limited to, the following:

- Clinically significant abnormal laboratory results or AEs, which rule out continuation of the study drug, as determined by the investigator or the sponsor.
- The investigator believes it is in the best interest of the subject.

- The subject requests withdrawal from the study.
- Eligibility criteria violation was noted after the subject started study drug and continuation of the study drug would place the subject at risk.
- Introduction of prohibited medications or dosages and continuation of the study drug would place the subject at risk.
- The subject becomes pregnant while on study drug.
- Subject is significantly noncompliant with study procedures, which would put the subject at risk for continued participation in the trial.
- Subject misses ≥ 4 consecutive days of study treatment.

For subjects to be considered lost to follow-up, reasonable attempts must be made to obtain information on the subject's final status. At a minimum, 2 telephone calls must be made and 1 certified letter must be sent and documented in the subject's source documentation.

AbbVie may terminate this study prematurely, either in its entirety or at any site. The investigator may also stop the study at his/her site if he/she has safety concerns. If AbbVie terminates the study for safety reasons, AbbVie will promptly notify the investigator.

COVID-19 Pandemic-Related Acceptable Protocol Modification

During the COVID-19 pandemic, it has been necessary to employ mitigation strategies to enable the investigator to ensure subject safety and continuity of care. Acceptable mitigation strategies are identified and included in the Operations Manual in [Appendix F](#).

The investigator should contact the AbbVie Therapeutic Area Medical Director (TA MD) before discontinuing a subject from the study for a reason other than described in the protocol to ensure all acceptable mitigation steps have been explored.

5.6 Follow-Up After Subject Discontinuation of Study Drug or from Study

Subjects who discontinue study treatment during the DBP or the BEP of the study will undertake the examinations and observations for the PD visit. Allowable time window for scheduled examination is within 3 days from the last administration of study drug (or within 14 days for the ophthalmologic examination). Subjects who discontinued study treatment during the DBP or the BEP will enter the safety follow-up period. For subjects who prematurely discontinue the safety follow-up period, the visit window for the PD visit is within 7 days after discontinuation.

If a subject prematurely discontinues study participation (withdrawal of informed consent), the procedures outlined for the PD visit should be completed within 3 days of the last administration of study drug. Subjects should be advised on the continued scientific importance of their data even if they discontinue treatment with study drug early. In addition, if a subject is willing, a 30-day follow-up phone call after the last dose of study drug may be completed to ensure all treatment-emergent AEs (TEAEs)/serious adverse events (SAEs) have been resolved.

5.7 Study Drug

Cariprazine and/or matching placebo manufactured by AbbVie will be taken orally once daily beginning on Day 1 (baseline; Visit 2) and should be taken at approximately the same time each day. The study drug can be taken with or without food. If subjects should forget to take their study drug at their regularly scheduled dosing time, they should take the next dose at the next scheduled dosing time.

AbbVie will provide study drug for cariprazine and matching placebo. AbbVie provided study drug should not be substituted or alternately sourced unless otherwise directed by AbbVie.

Cariprazine and matching placebo will be packaged in blister cards with quantities sufficient to accommodate study design. Each kit will be labeled per local requirements and this label must remain affixed to the kit. Upon receipt, study drug should be stored as specified on the label and kept in a secure location. Each kit will contain a unique kit number. This kit number is assigned to a subject via interactive response technology (IRT) and encodes the appropriate study drug to be dispensed at the subject's corresponding study visit. Site staff will complete all blank spaces on the label before dispensing to subjects. Study drug will only be used for the conduct of this study.

Table 2. Study Drug Information

	Investigational Product	Investigational Product Placebo
Investigational Product Name	Cariprazine	Matching placebo
Mode/Route of Administration (ROA)	Oral administration	Oral administration
Formulation	Capsule	Identically appearing capsule
Dosage Form	1.5 or 3 mg	Identically appearing placebo capsules
Dose and Frequency of Administrations	1.5, 3, or 6 mg once daily	N.A., placebo once daily
Drug Preparation/Packaging	Capsules will be provided in blister cards and labeled per local Regulatory requirements	Capsules will be provided in blister cards and labeled per local Regulatory requirements
Masking	Blinded	Blinded
Storage Conditions	Store between 20°C to 25°C (68°F to 77°F). Excursions permitted to 15° - 30°C (59° - 86°F).	Store between 20°C to 25°C (68°F to 77°F). Excursions permitted to 15° - 30°C (59° - 86°F).
Additional Information	N/A	N/A

5.8 Randomization/Drug Assignment

All subjects will be assigned a unique identification number by the IRT at screening (Visit 1). Subjects will be randomized to either the placebo arm or the cariprazine 6 mg/day arm in a 1:1 ratio on Day 1 (Visit 2). The IRT will assign a randomization number that will encode the subject's treatment group assignment according to the randomization schedule.

All AbbVie personnel with direct oversight of the conduct and management of the trial (with the exception of AbbVie Drug Supply Management Team) will remain blinded to each subject's treatment until the database lock after DBP. The investigator, study site personnel, and the subject will remain blinded to each subject's treatment throughout the study. To maintain the blind, the cariprazine capsules and placebo capsules provided for the study will be identical in appearance. The IRT will provide access to unblinded subject treatment information in the case of a medical emergency.

5.9 Protocol Deviations

AbbVie does not allow intentional/prospective deviations from the protocol except when necessary to eliminate an immediate hazard to study subjects. The investigator is responsible for complying with all protocol requirements, written instructions, and applicable laws regarding protocol deviations. If a protocol deviation occurs (or is identified, including those that may be due to the COVID-19 pandemic), the investigator is responsible for notifying IEC/independent review board (IRB), regulatory authorities (as applicable), and AbbVie.

5.10 Data Monitoring Committee

A data monitoring committee is not planned for this study. Given that the safety and AE profile of cariprazine has been characterized extensively in studies of both global and Asian populations, the emergence of new AEs affecting subject safety are not anticipated.

A population PK analysis demonstrated about 34% increase in steady-state exposure (area under the concentration time curve from time 0 to 24 hours [AUC_{0-24}]) of total cariprazine in Asian patients (mostly patients from studies that were conducted in India) compared to Caucasian patients. Japanese patients had on average 21% greater steady-state AUC_{0-24} than Caucasian patients (Study RGH-MS-08). These differences are within the observed cariprazine PK variability, are relatively small, and are not clinically relevant. The well characterized safety profile, coupled with data specific to the population of this study, means new safety AEs are not anticipated, and a Data Monitoring Committee is therefore not indicated.

6 SAFETY CONSIDERATIONS

6.1 Complaints and Adverse Events

Complaints

A complaint is any written, electronic, or oral communication that alleges deficiencies related to the physical characteristics, identity, quality, purity, potency, durability, reliability, safety, effectiveness, or performance of a product/device. Complaints associated with any component of this investigational product must be reported to AbbVie.

Product Complaint

A product complaint is any complaint related to the biologic or drug component of the product or to the medical device component(s).

For a product this may include, but is not limited to, damaged/broken product or packaging, product appearance whose color/markings do not match the labeling, labeling discrepancies/inadequacies in the labeling/instructions (e.g., printing illegible), missing components/product, device damage or not working properly, or packaging issues.

Product complaints concerning the investigational product and/or device must be reported to AbbVie within 24 hours of the study site's knowledge of the event.

Reporting will be done via electronic data capture (EDC). The date the product complaint details are entered into EDC and the form is saved represents the date reported to AbbVie. A back-up paper form will be provided for reporting complaints related to unassigned product or in the event of an EDC system issue. If a back-up paper form is used, the date the form is emailed to [contact] represents the date reported to AbbVie.

All follow-up information is to be reported to the sponsor (or an authorized representative) and documented in source as required by the sponsor. Product complaints associated with AEs will be reported in the study summary. All other complaints will be monitored on an ongoing basis. Product complaints occurring during the study will be followed up to a satisfactory conclusion.

Medical Complaints/Adverse Events and Serious Adverse Events: Cariprazine

An AE is defined as any untoward medical occurrence in a subject or clinical investigation subject administered a pharmaceutical product and which does not necessarily have a causal relationship with this treatment. An AE can therefore be any unfavorable and unintended sign (including an abnormal laboratory finding), symptom, or disease temporally associated with the use of a medicinal (investigational) product, whether or not the event is considered causally related to the use of the product.

Such an event can result from use of the drug as stipulated in the protocol or labeling, as well as from "special situations" such as accidental or intentional overdose, medication error, occupational or accidental exposure, off-label use, drug abuse, drug misuse, or drug withdrawal, all which must be reported whether associated with an AE or not. Any worsening of a pre-existing condition or illness is considered an AE. Worsening in severity of a reported AE should be reported as a new AE. Laboratory abnormalities and changes in vital signs are considered to be AEs only if they result in discontinuation from the study, necessitate therapeutic medical intervention, meets protocol-specific criteria, and/or if the investigator considers them to be AEs.

The investigators will monitor each subject for clinical and laboratory evidence of AEs on a routine basis throughout the study. All AEs will be followed to a satisfactory conclusion.

An elective surgery/procedure scheduled to occur during a study will not be considered an AE if the surgery/procedure is being performed for a pre-existing condition and/or the surgery/procedure has been pre-planned prior to study entry. However, if the pre-existing condition deteriorates unexpectedly during the study (e.g., surgery performed earlier than planned), then the deterioration of the condition for which the elective surgery/procedure is being done will be considered an AE.

If an AE, whether associated with study drug or not, meets any of the following criteria, it is to be reported to AbbVie clinical pharmacovigilance as a serious AE within 24 hours of the site being made

aware of the serious AE (refer to Section 4.2 of the Operations Manual for reporting details and contact information):

Death of Subject	An event that results in the death of a subject.
Life-Threatening	An event that, in the opinion of the investigator, would have resulted in immediate fatality if medical intervention had not been taken. This does not include an event that would have been fatal if it had occurred in a more severe form.
Hospitalization or Prolongation of Hospitalization	An event that results in an admission to the hospital for any length of time or prolongs the subject's hospital stay. This does not include an emergency room visit or admission to an outpatient facility.
Congenital Anomaly	An anomaly detected at or after birth, or any anomaly that results in fetal loss.
Persistent or Significant Disability/Incapacity	An event that results in a condition that substantially interferes with the activities of daily living of a study subject. Disability is not intended to include experiences of relatively minor medical significance such as headache, nausea, vomiting, diarrhea, influenza, and accidental trauma (e.g., sprained ankle).
Important Medical Event Requiring Medical or Surgical Intervention to Prevent Serious Outcome	An important medical event that may not be immediately life-threatening or result in death or hospitalization, but based on medical judgment may jeopardize the subject and may require medical or surgical intervention to prevent any of the outcomes listed above (i.e., death of subject, life threatening, hospitalization, prolongation of hospitalization, congenital anomaly, or persistent or significant disability/incapacity). Additionally, any elective or spontaneous abortion or stillbirth is considered an important medical event.

All AEs reported from the time of study drug administration until 8 weeks after discontinuation of study drug administration will be collected, whether solicited or spontaneously reported by the subject. In addition, study procedure-related serious and nonserious AEs will be collected from the time the subject signs the study-specific informed consent.

The following definitions will be used for Serious Adverse Reactions (SAR) and Suspected Unexpected Serious Adverse Reaction (SUSAR):

SAR	Defined as all noxious and unintended responses to an IMP related to any dose administered that result in an SAE as defined above.
------------	--

SUSAR	Refers to individual SAE case reports from clinical trials where a causal relationship between the SAE and the IMP was suspected by either the sponsor or the investigator, is unexpected (not listed in the applicable Reference Safety Information), and meets 1 of the above serious criteria.
--------------	---

AbbVie will be responsible for SUSAR reporting for the Investigational Medicinal Product (IMP) in accordance with global and local requirements.

Adverse events will be monitored throughout the study to identify any of special interest that may indicate a trend or risk to subjects.

Adverse Events of Special Interest

The following AEs of special interest will be monitored during the study:

- Akathisia and EPS
- The following are considered ocular AEs of special interest, whether serious or nonserious, and are required to be reported within 24 hours of the site being made aware:
 - cataract, lens, or lenticular abnormality or change, opacity, opacification or opalescence
 - blindness, night blindness, visual acuity or vision decrease, abnormality or change, visual acuity test abnormality or change
 - retinal, macular, or optic nerve degeneration, abnormality or change; retinal pigment epithelium detachment, abnormality or change

Adverse Event Severity and Relationship to Study Drug

The investigators will rate the severity of each AE as mild, moderate, or severe using the following definitions:

Mild	The AE is transient and easily tolerated by the subject.
Moderate	The AE causes the subject discomfort and interrupts the subject's usual activities.
Severe	The AE causes considerable interference with the subject's usual activities and may be incapacitating or life-threatening.

The investigator will use the following definitions to assess the relationship of the AE to the use of study drug:

Reasonable Possibility	After consideration of factors including timing of the event, biologic plausibility, clinical judgment, and potential alternative causes, there is sufficient evidence (information) to suggest a causal relationship.
-------------------------------	--

No Reasonable Possibility	After consideration of factors including timing of the event, biologic plausibility, clinical judgment, and potential alternative causes, there is insufficient evidence (information) to suggest a causal relationship.
----------------------------------	--

An AE is defined as any untoward medical occurrence, unintended disease or injury or any untoward clinical signs (including an abnormal laboratory finding) in subjects, users, or other persons whether or not related to the investigational medical device. This definition includes events related to the investigational medical device or comparator and events related to the procedures involved.

If an AE meets any of the following criteria, it is to be reported to AbbVie as an SAE within 24 hours after the site is made aware of the SAE:

- Led to death, injury, or permanent impairment to a body structure or body function
- Led to a serious deterioration in the health of a subject that either resulted in:
 - a life-threatening illness or injury, or
 - a permanent impairment of a body structure or a body function, or
 - inpatient hospitalization or prolongation of existing hospitalization, or
 - medical or surgical intervention to prevent life-threatening illness
 - chronic disease
- Led to fetal distress, fetal death, or a congenital abnormality or birth defect.

A planned hospitalization for a preexisting condition, or a procedure required by the protocol, without a serious deterioration in health, is not considered an SAE.

Pregnancy

While not an AE, pregnancy in a study subject must be reported to AbbVie within 24 hours after the site becomes aware of the pregnancy. Subjects who become pregnant during the study must be discontinued (Section 5.5). If a pregnancy occurs in a study subject or in the partner of a study subject, information regarding the pregnancy and the outcome will be collected.

In the event of pregnancy occurring in a subject's partner during the study, written informed consent from the partner must be obtained prior to collection of any such information. AbbVie will provide a separate consent form for this purpose. Pregnancy in a subject's partners will be collected from the date of the first dose through 12 weeks following the last dose of study drug. After all study visits, pregnancy should be followed up as spontaneously reported by the subject.

The pregnancy outcome of an elective or spontaneous abortion, stillbirth, or congenital anomaly is considered a SAE and must be reported to AbbVie within 24 hours after the site becomes aware of the event.

Potential Hy's Law Cases

Criteria for potential Hy's Law cases are as follows:

- ALT or AST $\geq 3 \times$ ULN AND
- Total bilirubin $\geq 2 \times$ ULN AND
- Alkaline phosphatase $< 2 \times$ ULN

Typically, all 3 analytes will be obtained from the same sample, but they may come from multiple samples taken within a 24-hour period.

A laboratory alert for potential Hy's Law cases will be in place, and will notify investigators and the sponsor immediately when the above criteria have been met. A potential Hy's Law case must be consulted with the AbbVie TA MD as soon as possible (within 24 hours of learning of the potential Hy's Law).

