10.2.4 Deaths, Serious Adverse Events, and Adverse Events Leading to Study Drug Discontinuation

Treatment-emergent serious AEs (SAEs), TEAEs leading to premature discontinuation of study drug, and TEAEs leading to death will be summarized by SOC and PT and in listing format. AEs during Safety follow-up will also be summarized in the same manner as TEAEs except for AEs leading to premature discontinuation of study drug.

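### Protocol 6.1 defines an SAE twice; the second, device-style list makes any AE that led to injury serious and lies outside the SUSAR cross-reference

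*Protocol*

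**What the plan says.** Protocol 6.1 sets the seriousness criteria in two places.

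The first is the table for cariprazine AEs (List 1 below). If an AE meets any criterion, whether or not it is linked to study drug, "it is to be reported to AbbVie clinical pharmacovigilance as a serious AE within 24 hours of the site being made" aware. The criteria are death, life-threatening event, hospitalization, congenital anomaly, persistent or significant disability, and important medical event. Hospitalization is "An event that results in an admission to the hospital for any length of time", or one that prolongs a stay. For disability the table adds: "Disability is not intended to include experiences of relatively minor medical significance". A sprained ankle is among its examples.

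The SAR and SUSAR definitions come next. To be a SUSAR, an event must be one that "meets 1 of the above serious criteria".

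The second place follows the severity and causality scales (List 2 below). It opens with a new AE definition: "This definition includes events related to the investigational medical device or comparator". It then repeats the 24-hour rule for any AE, with other criteria. The first of these is "Led to death, injury, or permanent impairment to a body structure or body function". The others are a serious deterioration in health with one of several results, and fetal distress, fetal death or a birth defect. A closing sentence excludes planned hospitalization and protocol-required procedures unless health seriously deteriorates. Table 2 in Protocol 5.7 lists only capsules.

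In the SAP, the overview in 10.2.2 has a row for serious TEAEs. Section 10.2.4 gives "Treatment-emergent serious AEs (SAEs), TEAEs leading to premature discontinuation of study drug, and TEAEs leading to death" by SOC and PT and as listings. Neither section says what makes an event serious.

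**The concern.** An SAE table can be read only if one rule decides what enters it. Here two rules apply to every AE, neither is ranked above the other, and nothing confines the second to device events. Part of the second conflicts with the first: one treats minor trauma as too slight to count as disability, and the other, on its face, makes any injury serious.

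Two things are at stake. The serious-TEAE counts by arm could include minor injuries reported under the second list. And the protocol's expedited-reporting definitions do not cover the same set of events as its SAE definitions. Safety and tolerability are part of the primary objective, and the SAP has reduced efficacy to descriptive statistics, so the safety tables should rest on a clear definition.

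**Working it through.** The documents give no event rate to recompute, so the check is a comparison of text.

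**Step 1. Do both rules operate?** Yes. Each tells the site to report within 24 hours any AE that meets any of its criteria. No sentence limits List 2 to device events or says which list prevails.

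**Step 2. Side by side.**

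| Topic | List 1 | List 2 |
|---|---|---|
| Injury | No separate criterion; minor trauma is kept out of disability | Free-standing, no severity limit |
| Chronic disease | Not named | Only as a result of serious deterioration in health |
| Fetal distress | Not named | Named |
| Hospitalization | Any admission, any length | Only with serious deterioration in health |
| Important medical event | General criterion | No general criterion; under serious deterioration, intervention to avert life-threatening illness covers part of it |
| Planned stay or protocol procedure | No such sentence in the table | Excluded unless health seriously deteriorates |

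**Step 3. Combine them.** Meeting either list is enough, so the set of SAEs is List 1 or List 2. Where List 2 is broader (injury, fetal distress, chronic disease with serious deterioration), it adds events. Where it is narrower (hospitalization, important medical events), it removes nothing, because List 1 already makes those events serious. The narrower wording matters only if a site works from List 2 alone. As written, therefore, the effect runs in one direction: over-inclusion.

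**Step 4. The injury criterion.** Suppose injury is read together with the words about a body structure. A sprain is still an injury to a body structure. The sprained ankle that List 1 gives as too minor for disability thus meets List 2 literally.

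**Step 5. SAR and SUSAR.** Both definitions refer to seriousness as set out above them, and both stand between the lists. By position they reach List 1 only. An event serious only under List 2 is a 24-hour SAE that does not meet the SUSAR wording.

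**Step 6. Scale, for illustration.** SAP 1.0 gives 34 randomised. One subject moved into or out of the serious category is 1/34 = 2.9 percentage points overall. Arm sizes are not given. Two equal arms (assumed) hold 34/2 = 17, and one subject is 1/17 = 5.9 points. Three equal arms (assumed) hold 34/3, about 11, and one subject is 1/11 = 9.1 points. These figures do not bound the effect: the 3 mg/day arm was dropped during the trial and may be smaller than 11, and the denominator will be the safety population.

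**The case against.** The strongest reply is that this is leftover template text with little practical effect. Injury is listed beside death and permanent impairment, and the next criterion names life-threatening injury separately. That would be redundant if every injury were already serious, so an experienced site may read the word as serious injury. List 1 sends sites to Operations Manual section 4.2 for reporting details; that manual was not available for this review and may settle the matter. Any error would be over-reporting, SAEs are listed individually, and all TEAEs are tabulated anyway. SUSAR reporting follows global and local requirements whatever the wording.

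Most of this stands as a limit on size. It does not remove the contradiction: the restrictive reading of injury is reasonable, but the text does not state it.

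Some stronger readings are tempting and go beyond the documents:

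- A reader might infer that every difference between the lists can reclassify an event. Step 3 shows otherwise for hospitalization and important medical events, unless List 1 is ignored.
- A reader might infer that sites are in fact reporting falls and minor injuries as serious. No such event is shown, and a fall is not itself an injury.
- A reader might assume that the SAP counts events from an investigator's seriousness flag. The SAP does not say so; it leaves the source and definition unstated.
- A reader might infer that important reactions escape expedited reporting. The documents do not show this; the additions from List 2 are mainly minor injuries.

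**Conclusion.** The inconsistency is real and minor. Protocol 6.1 holds two unreconciled SAE definitions. The second does not fit a capsule-only trial, literally admits any injury, and is not reached by the SAR and SUSAR cross-references. The expected direction is over-inclusion in the serious-TEAE tables.

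The size cannot be estimated from the documents. The percentages in the working show only what one subject is worth under assumed arm sizes; they do not measure a distortion. The trial has been terminated and no hypothesis test of safety is planned, so no error rate or efficacy result is affected. The conclusion assumes that the Operations Manual contains no rule that decides between the lists.

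**What to change.** 1. Reconcile Protocol 6.1 into one SAE definition. Remove the device-style AE definition and the second list, so that the SAR and SUSAR references to criteria above them have one meaning. Keep the sentence on planned hospitalization and protocol-required procedures and attach it to the remaining definition, because Protocol 4.1 keeps subjects in hospital at least until Week 2.
2. Enrolment has ended, so a protocol clarification cannot change how sites have already reported. State in SAP 10.2.2 and 10.2.4 which definition the word serious follows.
3. Before the final lock, query sites in both directions: events reported as serious that meet only a List 2 criterion, and events not reported as serious that meet a List 1 criterion. A query in the first direction alone could only downgrade reported SAEs.
4. Keep every event reported as serious in the SAE listing, marked with the criterion it met, so that any reclassification is visible.

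The cost is a short clarification, one or two SAP sentences and a brief query round. A few events may move between the serious and non-serious tables; all TEAEs stay in the overall TEAE tables.
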